7 SAFETY ANALYSES

Safety analyses will be performed on the Treated Population. Safety evaluations will be based on the incidence, intensity, and type of adverse events, as well as on clinically significant changes in the patient's physical examination, vital signs, and clinical laboratory results. Safety variables will be tabulated and presented by study drug actually received.

Because there is no pre-specified safety outcome defined in terms of AEs, clinically relevant laboratory parameters, or vital signs, any formal comparisons between the treatment arms with respect to specific safety parameters will be post-hoc.

8 ADVERSE EVENTS

Each AE and SAE term recorded on the case report forms (CRFs) will be mapped to a preferred term (PT) using the MedDRA dictionary. The investigator will classify the severity of AEs and SAEs using the NCI CTCAE v4.0 and will assess the relationship of each event to study treatment.

All AEs and SAEs occurring on study will be listed by treatment drug, center, and patient. The frequency and percentages of patients with treatment-emergent adverse events (TEAEs) will be tabulated by system organ class (SOC) and PT, where treatment-emergent is defined as any AE that;

- occurs on or after Cycle 1/Day 1 and through the end of the study or, if serious, up through 30 days after the last dose of study treatment;
- is present before Cycle 1/Day 1 but worsens in intensity or the investigator subsequently considers treatment-related.

For the purpose of calculating treatment emergence and inclusion in summary tables, incomplete onset dates will be imputed as detailed in Appendix A – Imputation Rules for Missing Data. Summaries will display incidence by study drug received and total incidence, and PTs within each SOC will appear in decreasing order of total incidence as well as in alphabetical order. At each level of summarization, a patient will be counted only once for each AE, SOC, or PT experienced within that level.

Related TEAEs, serious TEAEs, Grade 3 or higher TEAEs, related serious TEAEs, related Grade 3 or higher TEAEs, and TEAEs resulting in discontinuation of study treatment will be similarly summarized. Summaries of TEAEs by relationship to the study treatment will also be prepared.

At each level of summarization, a patient will be counted only once for each AE, SOC, or PT experienced within that level. In the summation for AE severity, within each level of AE, SOC, or PT experienced, the one with the highest severity will be included. In the summation for AE's relationship to the study drug, within each level of AE, SOC, or PT experienced, the one with the closest relationship to the study drug will be included.

AEs will be summarized for the treatment that the patient last receives prior to the occurrence of the AEs.

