Treatment-emergent AEs through 30 days after last dose of study treatment will be summarized by Medical Dictionary for Regulatory Activities (MedDRA™), Version 13.1 (or higher), System Organ Class and preferred term. The incidences and percentages of patients experiencing each AE preferred term will be summarized with descriptive statistics. The severity of AEs will also be summarized by National Cancer Institute Common Terminology Criteria for Adverse Events (NCI-CTCAE), Version 4.0 (or higher) grade and by causality (relationship to study treatment). Grade 3 and 4 AEs, SAEs, and AEs leading to withdrawal, dose modification, or treatment discontinuation will also be summarized by preferred term. Laboratory results will be classified according to NCI-CTCAE, Version 4.0 (or higher). Laboratory results not corresponding to an NCI-CTCAE term will not be graded. Incidences of laboratory abnormalities will be summarized with descriptive statistics. Vital signs and physical examination results will be summarized with descriptive statistics.

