12.4 ADVERSE EVENTS (AE'S) AND TREATMENT EMERGENT ADVERSE EVENTS (TEAE'S)

All AEs and SAEs occurring on study will be listed by patient. The frequency and percentages of patients with treatment-emergent adverse events (TEAEs) will be tabulated by system organ class (SOC) and preferred term (PT), where treatment-emergent is defined as any AE that:

- Occurs after first dosing of study medication and through the end of the study or up through 30 days after the last dose of study treatment, or
- Is considered treatment-related regardless of the start date of the event, or
- Is present before first dosing of study medication but worsens in intensity or the investigator subsequently considers treatment-related.

TEAEs that are considered at least possibly related to study treatment will be tabulated as well as deaths, SAEs, and events resulting in treatment discontinuation.

AEs that occur after informed consent but before first dosing of study medication will not be summarized but will be listed.

At each level of summarization, a patient will be counted only once for each AE, SOC, or PT experienced within that level. In the summation for AE severity, within each level of AE, SOC, or PT experienced, the one with the highest severity will be included. In the summation for AE's relationship to the study drug, within each level of AE, SOC, or PT experienced, the one with the closest relationship to the study drug will be included.

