12.5.1 RECORDING OF ADVERSE EVENTS

All adverse events of any patient during the course of the study will be reported on the case report form, and the investigator will give his or her opinion as to the relationship of the adverse event to study drug treatment (i.e., whether the event is related or unrelated to study drug administration – either ublituximab and/or ibrutinib). If the adverse event is serious, it should be reported as soon as possible and no greater than 24 hours to the sponsor or designee. Other untoward events occurring in the framework of a clinical study are also to be recorded as AEs (i.e., AEs that occur prior to assignment of study treatment that are related to a protocol-mandated intervention, including invasive procedures such as biopsies, medication washout, or no treatment run-in).

All AEs regardless of seriousness or relationship to ublituximab or ibrutinib treatment spanning from Cycle 1/Day 1 until 30 calendar days after discontinuation or completion of either protocol-specific treatment as defined by the protocol for that patient, are to be recorded on the eCRF.

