12.5.3 HANDLING OF ADVERSE EVENTS

All adverse events resulting in discontinuation from the study should be followed until resolution or stabilization. Patients should be followed for AEs for 30 calendar days after discontinuation or completion of protocol-specific treatment (either ublituximab or ibrutinib). All new AEs occurring during this period must be reported and followed until resolution unless, in the opinion of the investigator, these values are not likely to improve because of the underlying disease. In this case, the investigators must record his or her reasoning for this decision in the patient's medical record and as a comment on the eCRF. After 30 days, only AEs, SAEs, or deaths assessed by the investigator as treatment related are to be reported.

UTX-IB-301

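### SAP Section 8 narrows the protocol's definition of a treatment-emergent adverse event without declaring it, and can leave some late events out of the safety tables

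*SAP*

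**What the plan says.** SAP Section 8 (Adverse Events) has two criteria for a TEAE. The first takes events from Cycle 1 Day 1 "through the end of the study or, if serious, up through 30 days after the last dose of study treatment". The second takes an event that "is present before Cycle 1/Day 1 but worsens in intensity or the investigator subsequently considers treatment-related".

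Protocol 12.4 has three criteria. The first takes events after first dosing "through the end of the study or up through 30 days after the last dose of study treatment", with no condition on seriousness. The second takes any event that "Is considered treatment-related regardless of the start date of the event". The third takes an event that "Is present before first dosing of study medication but worsens in intensity or the investigator subsequently considers treatment-related".

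Other parts of the protocol also use a 30-day window without a seriousness condition. The synopsis (Safety Analyses) states: "Treatment-emergent AEs through 30 days after last dose of study treatment will be summarized". Protocol 12.5.1 requires recording of "All AEs regardless of seriousness or relationship to ublituximab or ibrutinib treatment spanning from Cycle 1/Day 1 until 30 calendar days after discontinuation". For the later period, Protocol 12.5.3 states: "After 30 days, only AEs, SAEs, or deaths assessed by the investigator as treatment related are to be reported".

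SAP Section 2 says that the SAP is based on the protocol of 31 July 2017, the version that contains this text. SAP 4.5 addresses only changes made after database lock. No SAP section mentions or justifies a different TEAE definition.

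**The concern.** The SAP governs the tables, so its definition decides which events are counted. Compared with the protocol it makes two separate cuts: it restricts the 30-day post-dose window to serious events, and it removes the criterion for related events whatever their start date. The sites are asked to collect the events concerned, so data would be gathered and then not tabulated.

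The tables at stake are overall TEAE incidence, Grade 3 or higher, related, and related Grade 3 or higher. Serious is not the same as severe (Protocol 12.6.2 makes the distinction), so a Grade 3 event that meets no seriousness criterion can be lost. The second cut can also remove serious related events. In an open-label trial that adds a drug to a common backbone, these tables are the main description of what the added drug costs in toxicity.

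The SAP is also uneven within itself. For concomitant medications, SAP 5.6 uses a 30-day window after last dose with no such restriction. A drug started on day 20 for a non-serious event could therefore be tabulated while the event is not.

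**Working it through.** The plan gives no figure to reproduce, and no sample size, power or alpha is involved. The check compares the two definitions and then applies both to the same set of cases.

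**Step 1. The definitions side by side.**

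| Element | Protocol 12.4 | SAP Section 8 |
|---|---|---|
| Event up to end of study | counted | counted |
| Event after end of study, within 30 days of last dose | counted | counted only if serious |
| Related event, any start date | counted | no such criterion |
| Pre-dose event that worsens or is later judged related | counted | counted |

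**Step 2. The rules for events starting after first dose.** Let *d* be the day of onset after last dose and *E* the day of the patient's end of study after last dose. The *or* in the window is read as either limit being enough.

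- Protocol: count if *d* ≤ *E*, or *d* ≤ 30, or the event is related.
- SAP: count if *d* ≤ *E*, or (the event is serious and *d* ≤ 30).

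**Step 3. Enumeration.** The inputs are illustrative assumptions, not trial data: *E* = 0, 7, 14 or 90; *d* = 5, 20, 45 or 100; serious or not; related or not. That gives 4 × 4 × 2 × 2 = 64 cases. The rules disagree in these:

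| *E* | Non-serious, *E* < *d* ≤ 30 | Related, *d* > *E* and *d* > 30 | Total |
|---|---|---|---|
| 0 | 4 | 4 | 8 |
| 7 | 2 | 4 | 6 |
| 14 | 2 | 4 | 6 |
| 90 | 0 | 2 | 2 |
| All | 8 | 14 | 22 |

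In all 22 the protocol counts the event and the SAP does not. The counts describe the grid and say nothing about frequency in the trial. Two examples:

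- End of study on day 7, non-serious event on day 20. The protocol counts it; the SAP does not, whether or not it is related.
- End of study on day 14, related event on day 45. The protocol counts it; the SAP does not, even if it is serious.

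With *E* = 90 the rules agree for onsets on days 5, 20 and 45, and differ only for related events on day 100.

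**Step 4. Who can have *E* below 30.** Protocol 8.4 and 8.4.1 call for an end of study visit at withdrawal of consent or documented progression, without timing it against day 30. Patients who stop treatment without progression stay in follow-up (Protocol 6.1 and 6.4), so their non-serious events within 30 days normally fall before end of study and count under both rules. The first group of losses is therefore confined to patients who leave the study within 30 days of last dose.

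**The case against.** The strongest reply is that the SAP's first criterion already counts every event, serious or not, up to the end of the study, and neither document defines that term. If it means the end of the whole trial, few events are lost. Protocol 6.4 and 12.5.3 also keep patients under adverse-event follow-up for 30 days after last dose, so a patient could be regarded as on study until then. This stands as a limit: the loss is conditional on a patient-level reading. That reading has support, because the protocol schedules the end of study visit per patient. Under the trial-level reading the SAP's clause on serious events would do almost nothing, and the tables would run past the 30-day window in the synopsis.

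Second, the missing criterion is partly covered. Related events before end of study, and pre-dose events later judged related, are still counted. The protocol is not uniform either, since the synopsis statement carries no such criterion. This also stands; what remains is chiefly the late related events that Protocol 12.5.3 asks sites to report.

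Third, the effect is cushioned. SAP Section 8 lists all on-study events, SAP 8.1.2 tabulates laboratory shifts by worst grade, and SAP Section 7 plans no formal safety comparison. That is correct, but listings give no incidence by arm and do not replace the summary that the protocol promises.

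A reader might go further and infer that all non-serious events in the 30 days after treatment are lost, or that the loss favours one arm. The documents support neither. Patients in continued follow-up are unaffected on the first point, and nothing in the documents shows a difference between arms in the timing of study exit.

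**Conclusion.** The discrepancy is exact and undeclared. Followed as written, the SAP can only lose events that the protocol counts. On a patient-level reading of *end of the study*, the losses are non-serious events between a patient's end of study and day 30 after last dose, and related events, serious or not, after both end of study and day 30.

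The size cannot be derived. One could assume that 20 to 40 of the 120 patients leave the study on the day of last dose and multiply by 30 days to get 600 to 1,200 patient-days. However, neither document gives the 20 to 40 or says that exit falls on that day, and patient-days are not events. SAP 6.1.2.5 expects most patients in both arms to be progression-free at the primary ORR analysis, so the number affected then is likely to be small. It could grow in later analyses as more patients progress.

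The primary endpoint is untouched. The point is worth correcting because it concerns safety incidences, the data are already collected, and the change is cheap.

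**What to change.** In SAP Section 8, delete *if serious* and adopt the three criteria of Protocol 12.4 verbatim. Define *end of the study* at patient level, and state whether the window closes at the later of that date and 30 days after last dose. If the narrower definition is intended, declare it in the SAP as a departure from the protocol and give the reason.

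A shorter replacement, such as onset from first dose to 30 days after last dose plus any later related event, should be avoided. It would drop unrelated events recorded after day 30 but before end of study, and pre-dose events later judged related. It would then match neither document.

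The cost is minor SAP and programming work with no new data collection. Reported incidences may rise slightly.

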8.1 LABORATORY ASSESSMENTS

Laboratory data for hematology and serum chemistry tests will be reported in International Units. Individual values outside the central laboratory reference ranges will be identified (by "H" for high and "L" for low) in the data listings displaying the absolute values for each patient.

8.1.1.1 LOCAL LABORATORY ANALYSES

The following laboratory evaluations will be performed at a laboratory affiliated with the site:

• Hematologic profile will be performed at baseline and on Days 1, 2 (Arm A only for ublituximab), 8 & 15 of Cycle 1, Day 1 of Cycles 2-6, and every 3 cycles thereafter.

Hematologic Profile			
Hematocrit	Neutrophils	Platelet count	
Hemoglobin	Lymphocytes		
Erythrocyte count	Monocytes		
Absolute neutrophil count	Eosinophils		
Absolute leukocyte count	Basophils		

• Serum chemistry will be obtained at baseline and on Days 1, 8 & 15 of Cycle 1, Day 1 of Cycles 2-6, and every 3 cycles thereafter

Serum Chemistry				
Albumin	Creatinine	SGOT [AST]		
Alkaline phosphatase	Glucose	SGPT [ALT]		
Bicarbonate	LDH	Sodium		
BUN	Magnesium	Total bilirubin		
Calcium	Phosphorus	Total Protein		
Chloride	Potassium	Uric acid		

- Serum β-HCG test will be obtained within 3 days prior to the initiation of therapy for women of childbearing potential.
- Coagulation lab tests to include, PT, aPTT, and INR will be drawn at screening.
- Quantitative immunoglobulin (IgG, IgM, IgA, IgE) test will be obtained at pre-dose on Day 1 and Day 15 of Cycle 1, on Day 1 of Cycle 3 and Cycle 6.
- Urinalysis to be obtained at screening (dipstick for pH, protein, glucose, blood, nitrite, leukocytes.
- Beta2-microglobulin to be obtained at screening.
- Serum Virology at screening to include HBsAG, HBc antibody, HCV antibody, and CMV

8.1.1.2 CENTRAL LABORATORY ANALYSES

The following laboratory evaluations will be performed at a central laboratory contracted by the Sponsor:

- FISH analyses at screening for del(13q), del(11q), del(17p), and (12)trisomy, t(11:14), IgHV and p53 mutation
- Minimal Residual Disease negativity analyses in patients with documented PR or CR at response assessment intervals beginning at the Cycle 6 response assessment.

8.1.2 STATISTICAL ANALYSIS

Continuous laboratory test results will be summarized descriptively by study drug received for actual values and for changes from Cycle 1 Day 1. Visits to be summarized include all scheduled post-Cycle 1 Day 1 visits.

Shift from baseline tables for laboratory parameters will be presented. Categories will be based on CTCAE grade (where applicable) or by high/low flags (where CTCAE grades are not defined). Data will be analyzed at all post-Cycle 1 Day 1 visits, by worst grade post-Cycle 1 Day 1. Laboratory tests that have high and low abnormalities will be summarized separately for each direction (e.g., hypocalcemia and hypercalcemia).

Abnormalities in laboratory tests that the investigator considers clinically significant will be recorded and summarized as AEs.

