6.4 DISCONTINUATION FROM STUDY TREATMENT

Patients will be discontinued from study treatment for any of the following reasons:

- Disease progression
- Intolerable toxicity related to study drug
- Patient requests to withdraw consent or discontinue treatment
- Pregnancy
- Inability of the patient to comply with study requirements
- Conditions requiring therapeutic intervention not permitted by the protocol
- Non-compliance/lost to follow-up
- Investigator discretion
- Discontinuation of the study by the Sponsor

Patients who discontinue from study treatment (for reasons other than progressive disease) will continue to be followed for progression. **Every attempt to continue to follow the patient for progression should be made.**

After withdrawal from protocol treatment, patients should be followed for AEs for 30 calendar days after their last dose of either study drug. All new AEs occurring during this period must be reported and followed until resolution, unless, in the opinion of the investigator, these values are not likely to improve because of the underlying disease. In this case the investigators must record his or her reasoning for this decision in the patient's medical records and as a comment on the electronic Case Report Form (eCRF).

All patients who have CTCAE Grade 3 or 4 laboratory abnormalities at the time of withdrawal should be followed until the laboratory values have returned to Grade 1 or 2, unless in the opinion of the investigator, it is not likely that these values are to improve because of the underlying disease. In this

UTX-IB-301

case, the investigator must record his or her reasoning for making this decision in the patient's medical records and as a comment on the eCRF.

UTX-IB-301

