8.4 DOSE DELAYS/DOSE MODIFICATIONS

Patients should be assessed clinically for toxicity at each visit using the NCI CTCAE v4.0 (http://evs.nci.nih.gov/ftp1/CTCAE/CTCAE) grading scale. Dose delay and/or modification guidance is for adverse events considered at least possibly related to either ublituximab or ibrutinib. If cytopenias are deemed related to the underlying disease rather than study drug, dose modifications are not required, or are per investigator discretion.

A maximum four (4) week delay of treatment for recovery from toxicity is allowed to recover from hematologic toxicities to \leq Grade 3 or non-hematologic toxicities to \leq Grade 2 or to baseline level. If greater than a four (4) week delay is necessary, then the patient should discontinue treatment and continue to be followed for progression. If a patient withdraws consent or has documented progression, an end of study visit should be completed.

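### SAP 8.1.2 sets no end date for the worst-grade laboratory tables, so some off-drug values are tabulated under the study drug received

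*SAP*

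**What the plan says.** **Laboratory window.** SAP 8.1.2 states for the shift tables: "Data will be analyzed at all post-Cycle 1 Day 1 visits, by worst grade post-Cycle 1 Day 1". For the continuous summaries it states: "Visits to be summarized include all scheduled post-Cycle 1 Day 1 visits". Neither sentence names a last day. Protocol 12.5.2 counts abnormal values at any assessment after baseline, again without an end.

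**Grouping.** SAP section 7 states: "Safety variables will be tabulated and presented by study drug actually received". SAP 8.1.2 says the same of the continuous laboratory results. Section 7 also makes any formal safety comparison between arms post hoc.

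**Blood draws.** SAP 8.1.1.1 ties hematology and chemistry to treatment cycles. Table 2 in both documents also marks them at End of study. Protocol 8.4 sets the timing of that visit: "If a patient withdraws consent or has documented progression, an end of study visit should be completed". Protocol 6.4 adds: "All patients who have CTCAE Grade 3 or 4 laboratory abnormalities at the time of withdrawal should be followed", until they return to Grade 1 or 2.

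**Adverse events.** The Protocol synopsis states: "Treatment-emergent AEs through 30 days after last dose of study treatment will be summarized". Protocol 12.4 defines treatment-emergent events as running to the end of the study or "up through 30 days after the last dose of study treatment". Protocol 12.5.1 records all AEs until 30 days after treatment ends, and 12.5.3 limits later reports to treatment-related events. SAP section 8 runs to the end of the study and attaches the 30-day limit only to serious events.

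**The concern.** A worst-grade table keeps each patient's most extreme value, so one late draw is enough to move a patient into a higher column. If that draw is taken months after the last dose, at progression or during another treatment, the grade may reflect the disease or the later treatment. The table gives no sign of this.

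Describing the safety profile of adding ublituximab is a secondary objective. Protocol 9.1.1.1 lists neutropenia and thrombocytopenia among the common reactions to the single agent, so high-grade cytopenia by regimen is a table that readers will look at. With about 60 patients per arm, a few such patients could change the apparent difference. The laboratory and AE tables would also cover different periods without saying so.

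**Working it through.** The plan states no figure on this point, so there is nothing to reproduce. The check compares the texts, followed by an illustration of size.

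**1. Is there an end date anywhere?** None was found. SAP 8.1.2 and Protocol 12.5.2 are both open. The SAP does set limits elsewhere: concomitant medications stop 30 days after the last administration (5.6), and PFS is censored at new anticancer therapy (6.1.2.5, 6.2). No such rule is given for laboratory values.

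**2. Which off-drug values are collected?**
- End of study visit: hematology and chemistry are marked in Table 2.
- Follow-up of Grade 3 or 4 values present at withdrawal (Protocol 6.4). These patients already have a Grade 3 or 4 value, so this follow-up adds few new ones.
- Three-monthly follow-up: in Table 2 this interval appears only in the tumor evaluation row. The response criteria use blood counts (Protocol 10.5, 10.6), but no follow-up draw is scheduled.

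The End of study visit is therefore the main source.

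**3. For whom is that visit far from the last dose?** Patients treated until progression, and kept on drug while the IRC confirms it (Protocol 10.2), have it on or near treatment. Patients who stop for toxicity, for a delay of more than four weeks or by choice are followed until progression. Their visit can fall months later, and nothing excludes new therapy in between. Protocol 10.8 counts certain CLL-related falls in platelets or hemoglobin as progression, so this draw can coincide with disease-related cytopenia. The documents do not give the CTCAE cut-offs, so the grade of such a fall is left open.

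**4. Size, as an illustration only.** Added share at Grade 3 or higher = f × q × (1 − p).
- p: on-drug Grade 3 or 4 rate. The 13% to 29% given for neutropenia with ibrutinib is used (Protocol 9.2.1.1).
- f: share of patients with a draw outside an on-treatment window. Assumed 10% to 40%.
- q: chance that such a draw is a patient's first at Grade 3 or higher. Assumed 10% to 30%.
- Arm size: about 120 / 2 = 60 (SAP 3.6).

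| p | f | q | Added points | Patients of 60 |
|---|---|---|---|---|
| 0.29 | 0.10 | 0.10 | 0.7 | 0.4 |
| 0.13 | 0.10 | 0.30 | 2.6 | 1.6 |
| 0.29 | 0.20 | 0.30 | 4.3 | 2.6 |
| 0.13 | 0.20 | 0.30 | 5.2 | 3.1 |
| 0.13 | 0.40 | 0.30 | 10.4 | 6.3 |

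For the last row, 0.40 × 0.30 × 0.87 = 0.104, and 0.104 × 60 = 6.3. Neither f nor q is in the documents.

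**The case against.** Several objections stand and limit the point.

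- A reader might infer that off-drug counts are charged to the assigned regimen as toxicity. The documents do not support this. Results are grouped by study drug received, the tables are descriptive, and relatedness is assessed for AEs and not for table entries.
- A reader might infer routine blood draws every three months off drug, or after new therapy. None is scheduled. A value after new therapy is possible but not shown to be common.
- A reader might infer that the SAP holds AEs to 30 days while leaving laboratory data open. Its own definition in section 8 runs to the end of the study for non-serious events, and Protocol 12.4 can be read either way. The clear 30-day limits are in the Protocol synopsis and in the AE collection rules. Since unrelated events are not collected after 30 days, the AE and laboratory data still cover different periods.
- Most counts at progression in patients still on drug would fall inside a 30-day window anyway. SAP 6.1.2.5 expects most patients not to have progressed at the primary ORR analysis, so few End of study visits at progression would exist then.
- A 30-day limit can remove values drawn while ublituximab is still present, and only in Arm A. Protocol 3.2.2.1 reports measurable drug in at least one patient up to day 169, after an eighth infusion on day 50. If both days are on the same clock, that is 169 − 50 = 119 days later, under a different dosing schedule. This is a reason to show later values separately, not to leave the window open.

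None of this supplies the missing end date.

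**Conclusion.** The point holds in limited form. As written, the plan lets off-drug values set the worst laboratory grade for patients who stop study drug before progression, mainly through the End of study visit at later progression. The effect is confined to descriptive safety tables. The ORR test and the other hypothesis tests are untouched. That only a minority of patients is involved is inferred from treatment continuing until progression, not from a stated rate.

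The range of 0.4 to 6.3 patients per arm of 60 rests on assumed inputs. Its low end is negligible, and its high end would be noticeable beside a 13% to 29% on-drug rate. It is tempting to read a bias against one regimen into this. The documents do not say which arm will have more off-drug follow-up, so the direction is unknown. This is a worthwhile, cheap improvement, not a flaw that threatens the trial's conclusions.

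**What to change.** - In SAP 8.1.2, base the worst-grade and shift tables on values after first dose through 30 days after the last dose of any study drug, or to the start of new anticancer therapy if earlier. Say that the last dose is the later of the two drugs' last doses, because an Arm A patient may continue on one drug alone (Protocol 8.4.1).
- Tabulate or list later values separately by study drug received, so that late effects in Arm A remain visible.
- Reconcile the treatment-emergent window in SAP section 8 with the Protocol synopsis and Protocol 12.4, 12.5.1 and 12.5.3, so that the AE and laboratory tables state the same period.
- Leave SAP 8.2.2 and 8.2.4 as they are. They summarize vital signs and ECOG status by scheduled visit and use no worst-value rule.

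The cost is a sentence or two in the SAP, one date filter and one extra table or listing. No data are lost. The downside is that drug-related cytopenias first seen more than 30 days after the last dose leave the main table and appear only in the separate display and, where reported, as related AEs.
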